Intervention refinement: The research team will work to review Phase 1 data with participating practice leads and champions, Rural ACO leaders and transformation specialists, regional content experts, and the KPPEPR Board to come up with a set of 4-8 major recommendations for intervention. They will then review previously developed pilot KanSurvive materials and suggest refinements based on these major recommendations. The research team and staff will utilize these suggestions to refine and finalize the KanSurvive intervention for Phase 2 (See Figure 6, Suggested study schema).

4.6 Phase 2: Implementation of the cluster-randomized controlled trial, with delayed start control arm Figure 6: Suggested Study Schema

Practice Facilitation. Due to the complexity of translating evidence-based guidelines into practice, significant gaps continue to exist between research evidence and practice.(58, 59) Knowledge is rarely sufficient to support the adoption of EBP behavior,(60, 61) with didactic education or passive dissemination strategies largely ineffective. Practice facilitation has emerged as an effective practice change approach and will be a key implementation strategy in the proposed study. Taken literally, facilitation means “to make easier”. (56, 62)Practice facilitation is broadly defined as “a supportive service provided to a primary care practice by a trained individual or team of individuals. (63)These individuals use a range of organizational development, project management, quality improvement (QI), and practice improvement approaches and methods to build the internal capacity of a practice to help it engage in improvement activities over time and support it in reaching incremental and transformative improvement goals. This support may be provided onsite, virtually (through phone conferences and Webinars), or through a combination of onsite and virtual visits” (AHRQ, <https://pcmh.ahrq.gov/page/practice-facilitation>). Practice facilitators, also known as practice coaches or quality improvement coaches, are specially trained individuals who help practices engage in implementing guidelines and developing capacity for continuous quality improvement. (18)

Baskerville, Liddy, & Hogg (64) completed a systematic review and meta-analysis showing primary care practices are 2.76 (95% CI, 2.18–3.43) times more likely to adopt evidence-based guidelines through practice facilitation. Consistent with the strategies used in KanSurvive practice facilitation, all the systematic review studies included audit with feedback, practice consensus building, and goal setting as key components, as well as basing the change approach on the system level and the organization change on common quality improvement tools, such as plan-do-study-act. Many also incorporated collaborative meetings, most using resource intensive onsite meetings and a handful utilizing virtual meetings. We considered options including increasing onsite facilitation, but this proved cost prohibitive in terms of travel and time as facilitators traveled 2- 8 hours one-way in order to meet with practices. There was repetition with some training needs across practices which lends itself to group training. In addition, facilitators noted common process challenges across many sites and sought additional ways to share these “lessons

learned" across sites. The combined KansSurvive-ECHO and enhanced facilitation approach provides greater exposure to implementation strategies from the Expert Recommendations for Implementing Change (ERIC) project,(65) both in terms of number of strategies and duration of the strategies.

The Project ECHO telementoring approach was identified as an implementation strategy to enhance the onsite practice facilitation strategies. We anticipate that the blend of in-person and telehealth strategies will address barriers around cost and scalability. The increased dose of facilitation provided through ECHO will provide repetition of key principles and will develop a community of practice. ECHO benefits are associated with social learning theory, with participants learning from the expert panel and from one another. ECHO sessions will include brief practice updates as well as de-identified cases related to both guideline content and "how to" processes for clinic adoption and sustained use. De-identified quality improvement information will also be shared.

In this study we will use a delayed intervention control arm design to evaluate the effectiveness of a combined practice facilitation (KansSurvive) plus Project ECHO improvement model for improving survivorship care in rural primary care practice. Our group has used validated implementation frameworks, such as Damschroder's (2009) Consolidated Framework for Implementation Research (CFIR) and Proctor's (2011) taxonomy of implementation outcomes to (1) create a set of questions to assess organizational readiness and suitability for ECHO and (2) provide those who commit to Project ECHO with a checklist to support successful implementation. Using adaptations of I-PARIHS and CFIR constructs, we created ECHO-specific organizational readiness questions, as well as a process guide for implementation. Each consideration was mapped onto Proctor's (2011) implementation outcomes, and questions relating to the constructs were developed and reviewed for clarity. The Preimplementation list included 20 questions; most questions fall within Proctor's (2001) implementation outcome domains of "Appropriateness" and "Acceptability." The Process Checklist is a 26-item checklist to help launch an ECHO project; items map onto the constructs of Planning, Engaging, Executing, Reflecting, and Evaluating. Given that fidelity to the ECHO model is associated with robust outcomes, effective implementation is critical. These tools will enable practices to work through key considerations as they implement KansSurvive plus Project ECHO.

Evaluation: RE-AIM (66)

1. *Reach* measured as %Expressed Interest /%Enrolled. As a marker of reach, participation rates will be calculated as the total number of rural primary care practices who express interest in the program divided by the total number of rural primary care sites eligible. Percent enrolled will be calculated as the total number of rural primary care practices who complete enrollment procedures divided by the total number of rural primary care practices who expressed interest. *Structured Interviews with Non-participants*. Structured interviews will focus on identifying the barriers associated with lack of participation in KansSurvive-ECHO, as well as facilitators/solutions to these barriers.

2. *Effectiveness* will be measured as % change in electronic health record evidence of guideline concordant care from pre- to 6-months post- KansSurvive-ECHO in intervention versus delayed intervention control practices. Using baseline EHR assessments in charts of cancer survivors identified from hospital registries we will compare the pre- and post- percentages of these survivors with best practice alerts, orders sets, health maintenance modules or other tools that note specific survivorship care services that they should be receiving to meet guidelines (Table 3) (67-74)

3. *Adoption* will be measured by calculating the representativeness of the participating rural primary care practices. Specifically, participating rural primary care practices will be measured on their size and their patient panels and will be compared as a group to the overall data that is available for all rural primary care practices in the state of Kansas on these key variables to assess for the representativeness of participating practices.

4. *Implementation Consistency: In addition to project feasibility and acceptability, we will assess facilitators and barriers to KansSurvive adoption using the i-PARIHS framework (Aim 3). Fidelity:* We will refine KansSurvive fidelity assessment consistent with Schoenwald et al.(55): (1) identifying relevant components for monitoring across practice facilitation and ECHO components (e.g., specificity, necessity, degree of precision), (2) determining who would provide the ratings, (3) obtaining the ratings, and (4) creating a summary score for the ratings. We will monitor fidelity to the KansSurvive components, with checklists associated with practice facilitation from multiple perspectives (e.g., participating practice teams, facilitators, ECHO subject matter experts). *Attendance and Participation.* Percent attendance will be

calculated for each rural primary care practice as the percent of practice facilitation and ECHO sessions attended divided by the total number of sessions offered. For both groups' participation the amount of between session work completed (as a percent).

5. **Maintenance:** Our experienced team will conduct structured interviews with participating rural primary care practices to assess their ability to sustain key components of the KanSurvive ECHO program over time and maintain effects at 6-months, including policies and procedures to support the cancer survivorship guidelines. Identification of cancer survivors with breast, lung, colon and prostate cancer. In order to identify survivors under the care of a particular PCP, we will engage the local/affiliated hospital's tumor registry. A list of all primary care providers participating in the intervention will be compiled using several key fields: "following doctor" (primary care provider) and the type of cancer (breast, colon, lung, and prostate cancer). This PCP list will be given to local hospitals, which will run a report to identify all cancer survivors with breast, lung, colon and prostate cancer affiliated with the "following doctor". Additional variables from the tumor registry will include demographics, stage, treatment, treating oncologist. Each primary care provider participating in the intervention will receive their list of affiliated patients. (75)

Data extraction will be completed by an "honest broker" who will utilize a consistent algorithm across all EMR systems to record evidence of guideline concordant survivorship care through a HIPAA waiver to allow such data abstraction without consenting individual patients. Medical record extraction is considered the "gold standard" and will be the primary objective data source for this trial. Practice-level data gathered from participating practices will be recorded directly into a secure KUMC REDCap database which requires username and password verification. Only designated research staff will have access to research information. The data collection survey tool built in REDCap will be pilot tested internally and modified as needed to ensure clarity for the data collector.

Table 3: Measure change in EHR documentation Concordant with Evidence-based Cancer Screening by Diagnosis

Cancer Diagnosis	Breast	Lung	Colon	Prostate	EHR Documentation Baseline (Yes/No)	EHR Documentation Post (Yes/No)
Recommended screening based on diagnosis*	Mammogram (annual)	CT (annual)	Colonoscopy (frequency specified by risk)	PSA (annual or more frequent based on risk and time since diagnosis)		
Distress/Depression Screen (PHQ9) (annual)	X	X	X	X		
Lifestyle Recommendations	X	X	X	X		
Diet/exercise/smoking cessation (annual)						
Review of Family History of Cancer (one time)	X	X	X	X		
Evidence of Changes to "Problem List" (one time, cancer diagnosis or history of)	X	X	X	X		
Evidence of Changes to "Health Maintenance/Preventive Services" or "Order/Smart set" or "Smart Phrases" or "Annual Wellness Visits" Since Cancer Diagnosis (one time)	X	X	X	X		
Treated with Anthracycline Y or N**						
ECHO Cardiogram (frequency specified by risk) **						
Bone Mineral Density (treated with anti-hormone or androgen deprivation therapy) (frequency specified by risk) **						

*if not deemed medically necessary, is their clarification in EHR (e.g., due to type of cancer surgery - total colectomy or bilateral mastectomy)

** exploratory variables: applicable to subset of patients based on treatment exposure

Limitations and strengths to EHR data are inherent to this type of project. There will be cancer survivors missed by the method of using local hospital registries, however, >95% of referrals from our focus group primary care providers are to the same oncologist/practices (49), thus keeping missing cancer survivors to a minimum. Use of a trained honest broker for data extraction will reduce the confounder of a lack of familiarity with EHR and where to find documentation within the EHR also will eliminate potential bias within the practice and patient population.

Study Timeline

Phase/Activity	Year 1	Year 2	Year 3	Year 4	Year 5
----------------	--------	--------	--------	--------	--------

4.9 Dissemination and Future Plans:

Using the i-PARIHS and RE-AIM frameworks for evaluation, relevant findings will be submitted for abstract (poster or presentation) at regional and national meetings and to peer-reviewed

Patient & advisory board engagement	x	x	x	x	x	x	x	x	x	x
Phase 1	x	x	x							
Site recruitment	x	x								
Workflow analysis		x	x							
Assess practice & EHR capabilities + P30 rural supp		x	x							
Explore facilitators & barriers of successful process		x	x					x	x	
Finalize intervention & assessment tools			x	x						
Phase 2				x	x	x	x	x	x	x
Intervention				x	x	x	x			
Wave 1				x	x	x				
Wave 2						x	x	x		
Data extraction							x	x		
Evaluation							x	x		
Data analysis, Dissemination								x	x	
Identify opportunities-sustain community of practice								x	x	

Location where study will be performed: The study will be performed at KUMC sites. Research staff are located in [name]. Additionally, the rest of the research staff is being supported by the Masonic Cancer Alliance (MCA) located in [name]. Other study activities will be completed online through Project ECHO.

Collaboration (with another institution, if applicable): The MCA will provide research support to complete various phases of the protocol.

Personnel who will conduct the study, including: The sponsor and principal investigators for the study are [name], MPH and [name], MPH.

Assessment of Subject Safety and Development of a Data and Safety Monitoring Plan:

Since this study does not involve any therapeutic intervention we do not anticipate the need for any safety monitoring.

Informed consent process and timing of obtaining of consent: Participating clinics will provide verbal consent to confirm they will participate in the project.

Alternatives to Participation: any of the recruited clinics will have the option to participate or not as the study is completely voluntary.

Costs to Subjects: Participating clinics will not incur any cost while in the project. Participating clinics will get a total of \$1,500 as compensation for their time and participation.

Publication Plan: Results will be published as deemed appropriate by the investigators Drs. [name] and [name].

Bibliography / References / Literature Citation

1. US Census Bureau. Quick Facts: Kansas 2018 [cited 2018]. Available from: <https://www.census.gov/quickfacts/fact/table/ks/PST045217>

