
Specific Aim 2. Evaluate the effectiveness of KanSurvive-ECHO for enhancing evidence-based survivorship care for rural breast, colorectal, lung, and prostate cancer survivors. Hypothesis: Compared to delayed intervention control, rural primary care practices randomized to KanSurvive-ECHO will demonstrate greater concordance with evidence-based survivorship care guidelines as measured by a composition score determined by change in EHR documentation consistent with guideline concordant care.

Specific Aim 3: Utilizing the Integrated Promoting Action on Research Implementation in Health Services (i-PARIHS) framework (6) describe key facilitators and barriers to implementation of KanSurvive-ECHO including innovation, recipients, context, and facilitation. This novel project will provide a model for development of a community of practice using practice facilitation and Project ECHO to improve the management and follow-up of cancer survivors in the acute and extended phases of cancer survivorship.

B. Background and Significance

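### The Aim 2 effectiveness outcome is defined inconsistently, with no scoring rule in the supplied text; one of its wordings counts EHR tools, and the analysis section compares before with after, not arm with arm

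*Combined protocol and SAP*

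**What the plan says.** The Specific Aim 2 hypothesis compares practices randomised to KanSurvive-ECHO with delayed-intervention controls on concordance with survivorship guidelines, "as measured by a composition score determined by change in EHR documentation consistent with guideline concordant care". It names no items, weights or formula.

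Under Evaluation: RE-AIM, item 2 first defines Effectiveness as % "change in electronic health record evidence of guideline concordant care from pre- to 6-months post- KansSurvive-ECHO", in intervention versus control practices. Whether the percentage change is relative or in points is not stated. The next sentence compares pre and post percentages of "survivors with best practice alerts, orders sets, health maintenance modules or other tools that note specific survivorship care services that they should be receiving", and closes with a reference to Table 3.

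Table 3 is titled "Measure change in EHR documentation Concordant with Evidence-based Cancer Screening by Diagnosis" and records Yes or No at baseline and post. Its six non-exploratory rows are diagnosis-specific screening, a PHQ9 distress screen, lifestyle advice, family-history review, a change to the problem list, and a change to health maintenance, order sets, smart phrases or wellness visits. A footnote to the screening row asks whether the chart explains screening judged not medically necessary.

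ANALYSES, Quantitative Data, tests performance indicators before and after intervention by chi-square or Fisher tests, and surveillance rates by tumor type by Fisher tests. It is written in the past tense.

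**The concern.** The introductory text says that an earlier curriculum changed knowledge but left practice unchanged, and the account of the KanSurvive pilot reports difficulty in turning knowledge into practice. Aim 2 therefore has to distinguish more recorded care from more EHR structure. A tool showing that a mammogram is due is not evidence that it was done.

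The intervention works on the EHR directly. ECHO reinforces EHR processes (introductory text), practices set EHR-based improvement goals (Practice facilitation), and providers in the intervention receive lists of their survivors (RE-AIM item 5). A measure that counts tools lies close to the intervention itself.

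Two further things are at stake. With several definitions and no rule, the definition could be settled after the data are seen. And a pooled before/after test could present change over time as the Aim 2 result, although the hypothesis is about a difference between randomised arms and the heading of section 4.6 calls the trial cluster-randomized.

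**Working it through.** The plan gives no effect size, power calculation or baseline rate for this outcome, so there is no figure to reproduce. The check is a comparison of the texts, followed by a labelled illustration.

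**1. The statements side by side**

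| Place | Quantity | Combination rule | Comparison |
|---|---|---|---|
| Specific Aim 2 hypothesis | Composite of change in EHR documentation | Composite named, rule absent | Between arms |
| RE-AIM item 2, first sentence | Percentage change in EHR evidence of concordant care | None | Between arms, pre to 6 months post |
| RE-AIM item 2, second sentence | Percentage of survivors with a tool noting services due | Not needed | Pre with post |
| Table 3 | Yes/No for each row | None | Baseline with post |
| ANALYSES | Separate indicators; surveillance rates by tumor type | No composite | Before with after; arms and practices not mentioned |

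**2. Is a rule given elsewhere?** The only summary score in the text belongs to the fidelity ratings (RE-AIM item 4). The consistent algorithm (recruitment section and RE-AIM item 5) concerns data extraction, and its content is not given. Weights, a mean or all-or-none rule, and scoring of the screening footnote do not appear.

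**3. What Table 3 contains.** On my reading, four rows record a care action (screening, PHQ9, lifestyle, family history) and two record an EHR change (problem list; tools). The split is not perfect, because a wellness visit also satisfies the tool row.

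**4. Illustration on assumed values.** Assume an equal-weight mean of the six rows, with the four care-action rows unchanged. Then

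gain = (change in problem-list row + change in tool row) / 6.

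- Problem list 80% to 90%, tools 0% to 50%: (10 + 50)/6 = 10.0 points. The tool percentage in RE-AIM item 2 rises by up to 50 points. A four-row care-action mean changes by 0.
- Problem list 80% to 100%, tools 0% to 100%: (20 + 100)/6 = 20.0 points; care-action mean 0.
- The same 10.0-point gain is 60 row-points. If all of it came from care actions, their mean would rise 60/4 = 15.0 points.

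These are chosen cases, not bounds, and they are changes within one arm. They equal the arm difference only if control practices do not change. The near-zero tool baseline is borrowed from the pilot practices, where the recruitment section reports no such EHR mechanisms; baselines in the trial practices are not given.

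**5. The screening footnote.** If a note that screening is unnecessary scored as a success, and 10% of survivors (assumed) gained only that note, a four-item score would rise 10/4 = 2.5 points with no service added. Dropping the item from the denominator lessens this but does not abolish it. A survivor with 2 of 4 items documented and screening missing moves to 3/4 = 75.0% (+25.0 points) if the note is a success, and to 2/3 = 66.7% (+16.7 points) if the item is dropped.

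**6. Would ANALYSES expose a tool-only gain?** Surveillance rates cover the screening row. The indicator tests would cover the other three care-action rows if the indicators are the Table 3 rows, but that is not stated.

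**The case against.** The strongest reply is that the declared outcome is documentation. The hypothesis, the first sentence of RE-AIM item 2 and the title of Table 3 all say so. In a Hybrid Type II trial, EHR structure is a legitimate target. Section A1 argues that survivorship care will not become routine without information infrastructure, and Table 1 reports that a condition missing from the problem list escapes the provider's attention. The tool sentence also points to Table 3, where tools are one row of six, and the plural indicators in ANALYSES may already test each row. Finally, any care-action score is read from charts too, so better charting could raise it.

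Most of this stands. It supports reporting the EHR-change rows and keeping a documentation composite as a secondary result. It also means that no definition built on Table 3 measures delivery directly. It does not supply the missing rule, reconcile a composite between arms with separate before/after tests, or explain why a count of tools should carry the label of effectiveness.

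A reader might infer that the trial was built to measure tool uptake and cannot detect a change in care. The documents do not support that: four of the six non-exploratory rows are care actions, and surveillance rates are tested separately.

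**Conclusion.** The point holds in a limited form. The supplied text states the Aim 2 outcome in ways that do not agree, gives no rule for combining the Table 3 rows, and describes an analysis that matches neither the composite nor the between-arm hypothesis and makes no allowance for practices. The tool sentence, taken at its wording, can rise while documented care actions stay flat.

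The size is unknown. The 10.0 and 20.0 points above rest on assumed baselines, equal weights and my grouping of the rows; they show that the missing rule matters, not how much it will.

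Three stronger readings should be avoided. That no rule exists anywhere is not shown, because the supplied text is not the whole document and the extraction algorithm is not described. That flat care actions would go unseen is not shown, because the indicator tests may cover every row. That the definition was chosen after the data were seen does not follow from the past tense of ANALYSES. The point should be put right before Aim 2 is interpreted, but it does not invalidate the data collected.

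**What to change.** 1. Reword RE-AIM item 2 so that Effectiveness is one percentage per survivor: applicable non-exploratory care-action items documented, divided by those applicable, equally weighted, with change in percentage points. The items are diagnosis-specific screening, PHQ9, lifestyle advice and family history.
2. Where the chart documents screening as not medically necessary, remove that item from the denominator; do not score it as a success. Report removals by arm and time point, because removal itself depends on charting.
3. Apply the same look-back rule at baseline and post.
4. Report the problem-list and tool rows separately as implementation results (RE-AIM item 4), noting that wellness visits count in the tool row. A six-row documentation composite may stay as a secondary result, given the rationale in section A1 and Table 1.
5. Use this definition in the Specific Aim 2 hypothesis and in ANALYSES. For this outcome, replace the before/after tests with a between-arm comparison at follow-up, adjusted for baseline and accounting for practice clustering: practice-level ANCOVA, or a mixed model with a random practice effect and small-sample degrees of freedom.
6. State that the score still measures documentation of care. If the Study Timeline step that finalises the assessment tools is still open, fix the rule there. If outcome data have already been analysed, label the definition post hoc.

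The cost is wording and re-scoring of items already to be extracted, provided that dates for the look-back are available at both time points. The downside is that the effect on care actions is probably smaller than on tool presence, so power is lower.

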76. Centers for Disease Control. Cancer Registry Research Approval Process: Classification of States by Level of Approval Required2018.

ANALYSES

Quantitative Data:

- Differences in cancer survivorship performance indicators before and after intervention were assessed using Chi-square or Fisher Exact tests.
- Clinical characteristics are summarized with frequencies and percentages.
- Demographic and patient characteristics are summarized descriptively with respect to frequencies and percentages for categorical variables, and mean, standard deviation, median, minimum and maximum for continuous variables.
- Differences in surveillance rates by tumor types before and after intervention were assessed using Fisher Exact tests.
- Statistical tests were considered significant if $p < 0.05$.

Qualitative Data:

- Interview notes, transcripts of practice facilitation meetings, and field records were compiled and analyzed using the i-PARIHS framework to evaluate barriers and facilitators to implementation.
- A thematic network analysis was employed by first noting initial impressions.
- Transcripts were independently reviewed line-by-line and preliminary codes were applied to relevant passages.
- A coding framework was developed with clear code descriptions, organizing data into themes and sub-themes.
- This framework was systematically applied to all transcripts using Dedoose software to ensure consistent and meaningful codes across the dataset.

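### Three of the six core Table 3 items are one-time entries, so the uncontrolled before/after tests in the ANALYSES section lean toward improvement on them

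*Combined protocol and SAP*

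**What the plan says.** Table 3 lists six core items, each with a Yes/No column for baseline and for post; the rows on anthracycline exposure, echocardiogram and bone density are footnoted as exploratory. Three core items recur: screening by diagnosis, the distress/depression screen and lifestyle advice. Three are satisfied once: "Review of Family History of Cancer (one time"), "Evidence of Changes to 'Problem List' (one time, cancer diagnosis or history of"), and the health-maintenance/order-set/smart-phrase/wellness-visit row, which ends "Since Cancer Diagnosis (one time").

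The ANALYSES section (Quantitative Data) gives the test: "Differences in cancer survivorship performance indicators before and after intervention were assessed using Chi-square or Fisher Exact tests". Surveillance rates by tumor type are also tested before against after. It names no comparison between arms.

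The protocol body describes a different contrast. The Aim 2 hypothesis reads "Compared to delayed intervention control, rural primary care practices randomized to KanSurvive-ECHO will demonstrate greater concordance", and the Effectiveness paragraph under RE-AIM measures change from before to "6-months post- KansSurvive-ECHO in intervention versus delayed intervention control practices". That paragraph compares percentages before and after in what reads as one set of survivors' charts.

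**The concern.** A one-time item that is Yes at baseline stays Yes. Some charts that are No at baseline become Yes through routine visits, whether or not the practice received KanSurvive-ECHO. In a fixed set of charts the percentage can therefore only stay level or rise. Annual items differ, because a survivor can be up to date at one reading and overdue at the next.

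A test without a control arm cannot separate this accumulation from an effect. For half of the core items, by count, the resulting bias has a known direction, and it favours the intervention. At stake is whether a significant rise on these items can be read as evidence about KanSurvive-ECHO.

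**Working it through.** The documents give no baseline rate, accrual rate, power calculation or count of abstracted charts, so there is no planned figure to reproduce. The check asks how often the named test rejects when the intervention does nothing.

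**Inputs from the documents.** 20 practices; an average of 200 survivors per practice; significance at p<0.05.

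**Assumptions.** Two-sided test; 10 practices per arm; every chart abstracted, so 10 × 200 = 2,000 intervention charts; the same charts at both readings; any past entry counts. Baseline share *b* and half-yearly accrual *h* among undocumented charts are varied.

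**Step 1: drift with zero effect.** After *k* half-years, rise = (1 − b) × (1 − (1 − h)^k).
- b = 30%, h = 5%, k = 1: 0.70 × 0.05 = 3.5 points.
- b = 30%, h = 5%, k = 4: 0.70 × (1 − 0.95^4) = 0.70 × 0.1855 = 13.0 points.
- b = 50%, h = 2%, k = 1: 0.50 × 0.02 = 1.0 point.
- b = 50%, h = 2%, k = 4: 0.50 × (1 − 0.98^4) = 0.50 × 0.0776 = 3.9 points.

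**Step 2: rise needed for p<0.05.** For the uncorrected Chi-square with n charts per reading, z = rise / √(p(1 − p) × 2/n), where p is the pooled share. At b = 50% and n = 2,000, 62 newly documented charts are needed: p = (1,000 + 1,062)/4,000 = 0.5155, SE = √(0.5155 × 0.4845 × 0.001) = 0.0158, z = 0.031/0.0158 = 1.96. The same search gives 58 charts (2.9 points) at b = 30% and 49 charts (2.5 points) at b = 80%.

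**Step 3: rejection probability.** This is the exact binomial chance of reaching that count, with n(1 − b) undocumented charts and cumulative probability 1 − (1 − h)^k.

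| Charts | Baseline | Accrual per half-year | Half-years | Rise (points) | Rejects with zero effect |
|---|---|---|---|---|---|
| 2,000 | 30% | 5% | 1 | 3.5 | 94% |
| 2,000 | 30% | 5% | 4 | 13.0 | about 100% |
| 2,000 | 50% | 2% | 1 | 1.0 | about 0% |
| 2,000 | 50% | 2% | 4 | 3.9 | 97% |
| 2,000 | 50% | 5% | 1 | 2.5 | 5% |
| 2,000 | 50% | 5% | 2 | 4.9 | about 100% |
| 2,000 | 80% | 2% | 4 | 1.6 | about 0% |
| 500 | 50% | 2% | 4 | 3.9 | under 1% |

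Four half-years is the Study Timeline read as half-year columns: three for Wave 1 plus the six months to the post reading. A paired test would not help. When every change is No to Yes, an exact McNemar test reaches p = 2 × (1/2)^6 = 0.031 with six changed charts.

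**Step 4: the between-arm comparison.** Simulated with 10 against 10 practices of 200 charts and the same accrual in both arms (practice coefficient of variation 0.5, 1,500 runs), a t-test on practice-level change rejected 4.3% to 5.5% of the time. This held for baselines of 20%, 50% and 80% and total accrual from 2% to 20%. The drift cancels.

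**Step 5: timing.** On the half-year reading, Wave 1 occupies half-years 4 to 6 and Wave 2 half-years 6 to 8. Wave 1's six-months-post point falls in half-year 7, after Wave 2 has begun.

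**The case against.** A reader might infer that the plan would declare success even if KanSurvive-ECHO did nothing. The documents do not support that. They define statistical significance, not success, and the Aim 2 hypothesis is between arms. A false positive is also not assured, as the near-zero rows of the table show. The 2,000 charts are themselves an assumption, since the site-recruitment text describes practice volume and not how many charts are abstracted.

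One-directional movement is also partly inferred. Only the health-maintenance row states a lookback running from diagnosis. Evidence of a change to the problem list could be scored within a window, and a closed cohort is not stated outright. If new survivors enter the post sample, the percentage can fall: with 50% at baseline, 5% accrual and 20% newcomers documented at 20%, it becomes 0.8 × 0.525 + 0.2 × 0.2 = 46%. The recruitment section also reports that the pilot practices had no EHR tools for identifying survivors or guiding their care, which suggests low background accrual for part of the third item, though that item also covers wellness visits.

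Finally, the protocol body already promises the arm comparison that removes the drift, and its absence from the ANALYSES section affects every indicator. All of these points stand. They limit the size and certainty of the problem. They do not make an uncontrolled before/after test suitable for items that accumulate.

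**Conclusion.** The point holds in conditional form. Three of six core items are one-time entries. With the same charts and an ever-documented lookback, the tests in the ANALYSES section are biased toward improvement on those items. The size is not fixed by the documents: zero-effect rejection at 2,000 charts runs from about 0% to about 100% over plausible-looking assumptions, and is lower with fewer charts. The wider defect is that the ANALYSES section does not carry through the randomized comparison that the protocol body promises. The one-time items are where its absence has the clearest direction.

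It should not be said that half of the composite score is affected, because no composite formula or weighting is given. Charts already Yes at baseline dilute a between-arm contrast, but that costs power and is not bias.

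**What to change.** 1. In the ANALYSES section, make the between-arm comparison of change the test of effectiveness for all indicators. Treat practice as the randomized unit, and measure both arms over the same calendar interval. Keep the before/after tests as description.
2. In Table 3, state the lookback window for each one-time item, and state whether the post sample is the baseline cohort or also admits new survivors.
3. For the one-time items, compare arms among survivors without the entry at baseline, counting only entries dated after baseline. A separate sub-score for these items is optional once arms are compared.
4. Settle the comparison date. Either use date-stamped entries up to a date before control practices cross over, or reconcile the Study Timeline with the six-months-post endpoint.

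Items 1 to 3 are mainly wording, plus extraction of entry dates by the honest broker, assuming the EHR systems hold them. The price is a smaller denominator for three items. Item 4 may shorten the controlled follow-up or require a change to the timeline.
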